Protocol Synopsis

Title of study	Global Clinical Study on Ethnic Differences in Drug Metabolism Based on the Joint Statement by the Japanese, Chinese and Korean Ministers of Health Clinical Pharmacokinetic Study of Simvastatin in Healthy Adult Male Subjects (Study number ID: UMIN00003644)
Objective	To investigate whether or not there are ethnic differences in the pharmacokinetics (PK) of simvastatin in healthy adult Japanese, Chinese, Korean and Caucasian male subjects based on the same protocol among the four countries.
Design	Open-label, single administration study
Subject	
Healthy adult male volunteers are eligible. In Japan, China and Korea, the nationalities of these subjects should be the same as those of grandfathers, grandmothers, father and mother. In China, only the Han race is eligible. In the U.S., only European Caucasian is eligible.
 
In this study, the above healthy adult male volunteers who satisfy all of the following inclusion criteria and none of the following exclusion criteria are eligible.
 
[Inclusion criteria]
 
 1) Those who are capable of providing written informed consent. 2) Men aged 20 to 35 years at the time of signing informed consent. 3) BMI of 18.5 to <30.0 and body weight of 50.0 to 100.0 kg at screening. 4) Those who are determined by the investigator to be healthy in the screening test and eligible for the study. 
[Exclusion criteria]
 
 1) Organopathy involving the heart, lung, liver and/or kidney etc. 2) A history of diseases involving the heart, lung, kidney, blood (such as coagulation system disorder), central nervous system and metabolic system that may interfere with the study. 3) Hypothyroidism, genetic myopathy or family history of it, history of drug-induced myopathy 4) Hypersensitivity or allergies to drugs or food, etc. (Particularly, a history of allergy to or adverse reactions associated with statin-type antihyperlipidemia drugs) 5) Oral administration of drugs such as over-the-counter drugs within 1 week prior to the study drug administration, or taking any kind of health food/supplement, grapefruit, drink/food containing grapefruit from 2 week prior to the study drug administration to the day 2, or taking any kind of fruit juice, drink containing caffeine or green tea from 1day before the study drug administration to the day 2, or the necessity for using other medications before study completion. 6) Smokers or a smoking history within the last 6 months. (The cotinine test is performed, if necessary) 7) Drug abuse or suspicion of drug abuse. (The drug screening test is performed, if necessary) 8) Alcohol drinkers (daily alcohol intake* of 50 g or more). * Alcohol intake (g) = [alcohol content] × [amount of alcohol intake (mL)] × [0.8 (specific gravity: weight of 1 mL of alcohol)] Example: When drinking 1000 mL of beer (alcohol content: 5.5%), alcohol intake = 0.055 × 1000 × 0.8 = 44 g 9) Total bilirubin or direct bilirubin, AST, ALT and ALP is 1.5 times higher, or other liver and renal function tests items are 1.25 times higher than the upper limits of normal at the sites. 10) Blood sampling of 200 mL or more within 1 month prior to the study drug administration, blood component donation (plasma or platelet) within 2 weeks, or blood collection of 400 mL or more within 3 months. 11) Participation in a Phase I study of a drug containing a new active ingredient within 4 months prior to the study drug administration or another clinical study within 3 months, and being administered the investigational drug (within 1 month prior to the study drug administration for a patch test). However, even if the period is longer than these, those who are determined to be not eligible for enrollment in the study in consideration of the characteristics of the previous investigational drug. 12) Those who are determined by the investigator to be not suitable as subjects of the study.
Study drug	A film-coated white tablet containing simvastatin, equivalent to 20 mg simvastatin The same product lot will be used in Japan, China, Korea and the U.S.

Dosage and administration	
One 20 mg tablet of the study drug is orally administered with 150 mL of soft mineral water (hardness <100, Volvic®, etc.) after fasting for at least 10 hours. Water drinking is prohibited up to 2 hours after taking the study drug. The subjects can drink soft mineral water (hardness <100, Volvic®, etc.) up to 500 mL during a period from 2 to 4 hours after administration. Soft mineral water (hardness <100, Volvic®, etc.) is given during the study period. Food intake is not allowed up to 4 hours after administration.
 
The calories and the balance of three major nutrients (PFC balance) of the dinner on the day before administration and the first lunch and dinner after administration are unified among the countries as much as possible.

Endpoints	
PK endpoints
 
1) Plasma concentrations of simvastatin and its open acid form
 
[Blood sampling points]
 
Before administration (baseline), 0.5, 1, 1.5, 2, 3, 4, 5, 6, 8, 12 and 24 hours after administration (12 points in total)
 
[PK parameters to be calculated]
 
For each substance to be measured and total inhibitory substance concentration, model-independent parameters and parameters related to compartmental model are calculated.
 
The following parameters should be calculated for model-independent parameters.
 
Peak plasma concentration (C_{max}), time to peak plasma concentration (t_{max}), elimination half-life ($t_{1/2}$), area under the plasma concentration-time curve (AUC_{0-t}, $AUC_{0-\infty}$), mean residence time (MRT), apparent total clearance (CL/f) and volume of distribution (Vd/f)
 
Maximum plasma concentration ($C_{max, norm}$) and AUC ($AUC_{0-t, norm}$, $AUC_{0-\infty, norm}$) normalized to dose per body weight of each substance to be measured and total inhibitory substance concentration.
 
Gene analysis for polymorphism
 
 Gene analysis for polymorphism of the CYP3A4, CYP3A5, ABCB1, OATP1B1 and ABCG2 related to the pharmacokinetics of simvastatin. 
Safety endpoints
 
 Types, severity, onset date/time, duration, number of subjects, number of cases and incidence of adverse events that occurred after the study drug administration will be examined. For laboratory values, vital signs (body temperature, blood pressure and pulse rate) and body weight, basic statistics (mean and standard deviation) should be calculated by each test point.
Observation and tests	
1) Observation period: From the day of the study drug administration (Day 1) to discharge from the hospital (Day 2).
 
2) Tests: Physical examination findings (history taking, subjective symptoms, objective findings, auscultation, percussion), hematology, blood biochemistry, urinalysis, vital signs (body temperature, blood pressure and pulse rate) and body weight measurement

Target sample size	40 subjects for each country (160 subjects in total in Japan, China, Korea and the U.S.)
Planned study period	June 2010 to November 2010

Study Schedule

Date of study	Screening Within 30 days	Study														
		Day -1	Day 1										Day 2			
		Admission by 16:30	8:00	9:00	9:30	10:00	10:30	11:00	12:00	13:00	14:00	15:00	17:00	21:00	9:00	
Time			-1	0	0.5	1	1.5	2	3	4	5	6	8	12	24	
Time after oral administration (h)																
Admission/visit	Visit	Admission														
Informed consent																
Subject background characteristics																
Study drug administration																
Physical examination by the investigator																
Body weight																
Height																
Vital sign																
12-lead electrocardiography																
Adverse event																
Blood sampling	Gene polymorphism examination															
	Pharmacokinetics															
	Laboratory test															
	Infectious disease test															
Urine sampling	Laboratory tests															

Meal time during hospitalization: Morning of Day 1 is fasting. Follow the instruction on the meal time by the site other than the following.

1 day before administration (Day -1: at 19:00)

Day of administration (Day 1: Having a lunch after completion of blood sampling and tests at 4 hours after administration.)

1 day after administration (Day 2: Having a breakfast after completion of blood sampling and tests at 24 hours after administration.)

a): Collected specimens (e.g., EDTA-2Na added) will be refrigerated at -60°C or less, and sent to the institute for gene polymorphism analysis using dry ices within 2 weeks after sampling, if possible.

List of abbreviations

Abbreviation	Full expression
ABC	ATP-binding cassette (ATP-binding cassette) ABC transporter: gene ABCB1, gene ABCG2
ALP	alkaline phosphatase
ALT	alanine aminotransferase
AST	aspartate aminotransferase
AUC	area under the plasma concentration-time curve AUC _{0-t} : Area under the plasma concentration-time curve from time zero to the last blood sampling AUC _{0-∞} : Area under the plasma concentration-time curve from time zero to infinity
CK	creatine kinase
CL/f	apparent total clearance
C _{max}	peak concentration
CRP	C-reactive protein
CYP	Cytochrome P450: Collective term of hydroxylase family
f	bioavailability
γ-GTP	gamma glutamyl transpeptidase
HBs antigen	hepatitis B surface antigen
HCV antibody	anti-hepatitis C virus antibody
HDL	high density lipoprotein
HIV antibody	human immunodeficiency virus antibody
HMG-CoA	3-hydroxy-3-methylglutaryl-CoA
LDH	lactate dehydrogenase
LDL	low-density lipoprotein
MDR	multidrug resistance protein
MedDRA	Medical Dictionary for Regulatory Activities
MRT	mean residence time
OATP	organic anion-transporting polypeptide
PFC balance	Protein- Fat- Carbohydrate balance
t _{1/2}	half-life
t _{max}	time of peak concentration
Vd/f	volume of distribution

List of definitions of terms

Terms	Definition
Anonymized number that is linkable to subjects	The numbers are given to the subjects (anonymized). The record of the linkage of the numbers and the subjects is kept, if necessary to identify the subjects.

Table of contents

1. INTRODUCTION	2
2. STUDY OBJECTIVE	3
2.1 Endpoints	3
2.1.1 PK Endpoints	3
2.1.2 Gene polymorphism examination	3
2.1.3 Safety endpoints.....	3
3. STUDY TYPE AND DESIGN	4
3.1 Study Type.....	4
3.2 Study design	4
4. SUBJECTS	5
4.1 Inclusion criteria	5
4.2 Exclusion criteria	6
4.3 Discontinuation/withdrawal criteria.....	7
4.4 Procedures for discontinuation/withdrawal	7
5. STUDY DRUG	8
5.1 Supply of the Study Drug.....	8
5.2 Name of the Study Drug and Other Explanations.....	8
5.3 Control/Storage of the Study Drug	9
6. PROHIBITED CONCOMITANT MEDICATIONS	9
7. MANAGEMENT OF SUBJECTS	9
7.1 Management of Subjects in Each Period	9
7.2 Intake of health foods /supplement, grapefruit or drink/food containing grapefruit, fruit juce and drink containing caffeine and green tea	10
7.3 Eating and Drinking	10
7.4 Smoking	10
7.5 Physical exercise	11
7.6 Posture.....	11
8. OBSERVATIONS AND ENDPOINTS	12
8.1 Procedure for Study Implementation	12
8.1.1 Screening.....	12
8.1.2 Study	12
8.2 Investigations/evaluations.....	14
8.2.1 Evaluation items for the PK endpoints	14
8.2.2 Investigation items for gene polymorphism examination.....	15
8.2.3 Storage place/period and method of discard of specimens	16

1. INTRODUCTION

Lately, global clinical studies have been promoted from the perspectives of effective and prompt development of new drug and of solving drug lag issue. At the "First Meeting of the Japanese, Chinese and Korean Health Ministers" held in April 2007 in Seoul, the 3 countries worked on the clarification of racial and ethnic differences in clinical study data and ultimately agreed to aim at the mutual acceptance of clinical research data.

In consideration of this circumstance, Japan has analyzed ethnic difference by using existing clinical pharmacokinetic study data in the "Study Group for Evaluation of Ethnic Factors in Clinical Data in Japanese, Chinese and Korean Populations ([name] Group)". In response to the result of this research, in the "Global Clinical Study on Ethnic Differences in Drug Metabolism Based on the Announcement by the Japanese, Chinese and Korean Ministers of Health, Labor and Welfare ([name] Group)," a 2009 Health Labour Sciences Research Grants (Global-Scale Health Topic Promotion Research), implementation of a global pharmacokinetic study is planned with a study drug which has been selected based on evaluation results using existing data to collect supplemental data on ethnic difference or to improve data reliability.

Simvastatin, used as a study drug in this study, is a statin-type antihyperlipidemia drug which has been already marketed in all the countries. Its dosage is different, depending on countries, and the initial dose is 5 mg/day and maximum dose is 20 mg/day in Japan, while the initial dose range is 20-40 mg/day in Korea, China and the U.S. The initial doses in those countries are four times higher than that in Japan. The pharmacokinetic characteristics of simvastatin are as follows: Simvastatin is a prodrug, showing its pharmacological activity by changing to an open acid form in liver in humans. Simvastatin is metabolized mainly by CYP3A4/5 in the intestinal tract/liver, and its metabolites show their pharmacological activity, too. The pharmacokinetic parameters of unchanged simvastatin can be affected by functional change of CYP3A4/5 or OATP1B1 etc., drug transporters involved in hepatic uptake. Oral bioavailability is low, less than 5% as an open acid form. The elimination rate is about 60% in the feces and about 13% in urine, considered that simvastatin is mainly eliminated in bile. Comparison of existing pharmacokinetic data by the statistic process combining the results in Japanese and Western populations showed a large difference in the pharmacokinetics of simvastatin between Japanese and Western populations, but information on pharmacokinetics of simvastatin in East Asian population is insufficient due to the lack of the data on Chinese and Koreans. Considering these backgrounds, we decided to obtain the data on East Asian population and conduct a clinical pharmacokinetic study, according to the same protocol, in East Asian and Caucasian populations (as a reference), to examine the difference in pharmacokinetics of simvastatin among these populations.

2. STUDY OBJECTIVE

To investigate whether or not there are ethnic differences in the pharmacokinetics (PK) of simvastatin which has been already marketed in healthy adult Japanese, Chinese, Korean and Caucasian male subjects based on the same protocol among the four countries.

2.1 Endpoints

2.1.1 PK Endpoints

Plasma concentration of simvastatin and its open acid form.

[Blood sampling points]

Before administration (baseline), 0.5, 1, 1.5, 2, 3, 4, 5, 6, 8, 12 and 24 hours after administration (12 points in total)

[PK parameters to be calculated]

For each substance to be measured and total inhibitory substance concentration, model-independent parameters and parameters related to compartmental model are calculated.

The following parameters should be calculated for model-independent parameters.

Peak plasma concentration (C_{max}), time to peak plasma concentration (t_{max}), elimination half-life ($t_{1/2}$), area under the plasma concentration-time curve (AUC_{0-t} , $AUC_{0-\infty}$), mean residence time (MRT), apparent total clearance (CL/f) and volume of distribution (Vd/f)

Maximum plasma concentration ($C_{max, norm}$) and AUC ($AUC_{0-t, norm}$, $AUC_{0-\infty, norm}$) normalized to dose per body weight of each substance to be measured and total inhibitory substance concentration.

2.1.2 Gene polymorphism examination

- Gene analysis for polymorphism of the CYP3A4, CYP3A5, ABCB1, OATP1B1 and ABCG2 related to the pharmacokinetics of simvastatin.

[Reasons for choice]

Simvastatin is known to be metabolized by CYP3A4 and CYP3A5¹⁾. In addition, it is reported that pharmacokinetics of simvastatin are different, depending on polymorphism of the OATP1B1, involved with hepatic uptake of simvastatin from the blood²⁾. In addition, it is reported that pharmacokinetics are different, depending on polymorphism of the ABCB1 and ABCG2 that eliminate the drug from the liver to bile^{3, 4)}. Based on these, we will conduct the polymorphism analysis of these genes considered to affect pharmacokinetics of simvastatin.

2.1.3 Safety endpoints

- Types, severity, onset date/time, duration, number of subjects, number of cases and incidence of adverse events that occurred after the study drug administration will be examined.
- For laboratory values, vital signs (body temperature, blood pressure and pulse rate) and body weight, basic statistics (mean and standard deviation) should be calculated by each test point.

3. STUDY TYPE AND DESIGN

3.1 Study Type

An open-label and single administration study

3.2 Study design

The study design is described in Table 3-1.

Table 3-1 Study design

Method	Open-label, single administration study
Study drug	Simvastatin. The same product lot will be used in all the countries.
Target sample size	40 subjects for each country (160 subjects in total in Japan, China, Korea and the U.S.)
Dosage and administration	One 20 mg tablet of the study drug is orally administered with 150 mL of soft mineral water (hardness <100, Volvic®, etc.) after fasting for at least 10 hours. Water drinking is prohibited up to 2 hours after taking the study drug. The subjects can drink soft mineral water (hardness <100, Volvic®, etc.) up to 500 mL during a period from 2 to 4 hours after administration. Soft mineral water (hardness <100, Volvic®, etc.) is given during the study period. Food intake is not allowed up to 4 hours after administration. The calories and the balance of three major nutrients (PFC balance) of the dinner on the day before administration and the first lunch and dinner after administration are unified among the countries as much as possible.

[Rationales for selection]

Target sample size:

The number of subjects required to investigate ethnic differences in the pharmacokinetics was calculated⁵⁾. Based on the integration of the data, the difference in $AUC_{0-\infty}$ revealed about 60% between Japanese and Western populations, and the difference in $AUC_{0-\infty}$ was not expected among East Asian population from the data of rosuvastatin. Considering this information, the number of the patients was calculated to detect 40% difference in $AUC_{0-\infty}$ at least between East Asian and Western populations with a power of 80%. As a result, under the null hypothesis "There is no difference in PK among Japanese, Chinese, Korean and Caucasian" and the alternative hypothesis that at least one ethnic group shows the difference in the mean of pharmacokinetics, the number of subjects was calculated to be at least 25 subjects based on information of a 40 % and 20% difference in $AUC_{0-\infty}$ with a power of 80 % between Japanese and Western populations, and between Japanese and Chinese/Koreans, respectively. Since the analysis of gene polymorphism is performed after PK analysis. Based on this, the target sample size of this study was determined to be 40 subjects from each ethnic population, considering the subjects excluded from the results of analysis of CYP3A5 to be CYP3A5*3 homo, dropouts by

discontinuation or withdrawals.

The reason why the target sample size was approximately 1.5 times the number of subjects necessary for statistical analysis was based on information on ethnic differences of CYP3A5 polymorphism. According to the investigation⁶⁾, the frequency of CYP3A5*3 polymorphism was 0.7 to 0.77 in East Asian population and 0.85 to 0.95 in Caucasian population .

Dosage and administration: The dosage and administration was chosen to be within the range of those approved, and single oral administration of 20 mg, with which the plasma concentrations of simvastatin and its open acid form can be measured for a sufficient period of time, was selected.

In order to avoid a wide variation in absorption of study drug from the digestive track, the intake of water after administration of study drug, and calories and PFC balance at the dinner on the day before and the first lunch and dinner after administration were to be unified among all the four countries as much as possible.

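### Section 3.2 gives one figure, 80% power at 25 per group, to several different comparisons; if it belongs to the 40% contrast or the four-group test, the 20% Japanese–Chinese/Korean contrast falls well short of it

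*Protocol*

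**What the plan says.** All of this stands in the target sample size rationale of Protocol section 3.2.

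- The purpose is first given as detecting a 40% difference in AUC0-∞ "at least between East Asian and Western populations with a power of 80" percent.
- A single null hypothesis of no PK difference covers all four populations. It is set against "the alternative hypothesis that at least one ethnic group shows the difference in the mean of pharmacokinetics". That is a four-group (omnibus) test.
- Under those hypotheses, "the number of subjects was calculated to be at least 25 subjects", using differences of 40% and 20% "with a power of 80 % between Japanese and Western populations, and between Japanese and Chinese/Koreans, respectively".
- Just before this, a difference in AUC0-∞ "was not expected among East Asian population from the data of rosuvastatin", yet the calculation uses 20% within East Asia.
- The enrolment target is then raised: "the target sample size of this study was determined to be 40 subjects from each ethnic population". The increase allows for CYP3A5-related exclusions and dropouts.

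The 25 is not labelled per group. I read it that way because "the target sample size was approximately 1.5 times the number of subjects necessary for statistical analysis", and 40/25 = 1.6.

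**The concern.** Read as written, the 80% attaches to each named pair: 40% Japanese versus Western, and 20% Japanese versus Chinese or Korean. At equal variance the required number grows with the inverse square of the difference, so halving the difference needs about four times as many subjects. One number cannot be the 80% answer to both. The power of an omnibus test is a third quantity, and it is not the power of any single pair.

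The East Asian contrasts are central. The introduction (section 1) presents the study as work towards Japan, China and Korea accepting each other's data. It names the missing Chinese and Korean data as the gap, with Caucasians as a reference. A reader who believes a 20% East Asian difference has 80% power could take a non-significant result as good evidence of no such difference.

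**Working it through.** **Inputs from section 3.2:** 25 per group (inferred as above), four equal groups, differences of 40% and 20%, power 80%.

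**Assumptions:** two-sided 5% for t tests, 5% for the F test, and a common SD. Scale and direction are not stated, so I tried three versions: a raw scale (0.40 and 0.20 of the reference mean), log ratios 1.4/1.2, and log ratios 0.6/0.8.

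**The plan's figure.** The 25 cannot be reproduced without an SD. Each reading is therefore used to find the SD that makes 25 correct, and that SD is applied to the other comparisons.

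**A. The 25 was set by the 40% pairwise contrast.** The noncentrality is δ = d / (SD·√(2/n)). With n = 25 (48 df, critical t 2.011), 80% power needs δ = 2.859.
- SD = 0.40 / (2.859 × 0.2828) = 0.495.
- For 20%: δ = 0.20 / (0.495 × 0.2828) = 1.43, so power is 0.289.
- Reaching 80% for 20% would need 97 per group.

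**B. The 25 was set by the omnibus test.** The noncentrality is λ = n·Σ(μᵢ − μ̄)² / SD². With 3 and 96 df (critical F 2.699), 80% power needs λ = 11.36.
- Means 0/0.2/0.2/0.4 (Chinese and Koreans in between): Σ = 0.08, so SD = √(25 × 0.08 / 11.36) = 0.420. For 20%, δ = 1.685 and power on the pooled 96 df is 0.385. For 40%, power is 0.916.
- Means 0/−0.2/−0.2/0.4 (Chinese and Koreans on the other side of Japanese): Σ = 0.24, so SD = √(25 × 0.24 / 11.36) = 0.727. Power is 0.161 for 20% and 0.487 for 40%.

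**C. The 25 was set by the 20% pairwise contrast.** SD = 0.20 / (2.859 × 0.2828) = 0.247. Power for 40% at 25 per group then exceeds 0.99. Only 8 per group would be needed for 40% at 80% power, and 10 for the omnibus test.

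| Reading and scale | SD | 40% contrast, n = 25 | 20% contrast, n = 25 | 20% contrast, n = 40 |
|---|---|---|---|---|
| A, raw | 0.495 | 0.80 | 0.289 | 0.431 |
| A, log 1.4/1.2 | 0.416 | 0.80 | 0.330 | 0.490 |
| A, log 0.6/0.8 | 0.632 | 0.80 | 0.232 | 0.345 |
| B, raw, in between | 0.420 | 0.916 | 0.385 | 0.563 |
| B, log 1.4/1.2 | 0.354 | 0.915 | 0.438 | 0.630 |
| B, log 0.6/0.8 | 0.538 | 0.914 | 0.306 | 0.454 |
| B, raw, other side | 0.727 | 0.487 | 0.161 | 0.231 |

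Under C, the two log versions give SD 0.225 and 0.276, with 9 and 6 per group enough for 40%.

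**The case against.** The strongest reply is that the sentence is governed by one four-group null and alternative. On that view 40% and 20% are simply the assumed pattern of means, and the closing word pairs each difference with its populations. One sample size can give 80% for that pattern. This is a fair reading and may well be what was done. It does not rescue the wording, because omnibus power is then printed against two named pairs whose own power is different.

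A reader might go further and infer that no SD could give 80% for both pairs. The documents do not support that. The number is a minimum, and at an SD of about 0.25 or less both pairs have at least 80%. That route has a cost: about 8 per group would then answer the 40% question, so 25 would not be the number calculated to detect 40% with 80% power.

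A reader might also infer that the East Asian–Western sentence must be wrong because Chinese and Koreans would sit only 20% from Western subjects. That needs a direction the protocol does not give. On the raw scale the gap is 20% one way and 60% the other.

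Finally, the calculation cites a reference that is not at hand, and the text ends before section 10. The missing SD and alpha are therefore not held against the plan. They are only the reason the power figures are conditional.

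**Conclusion.** The point stands as an inconsistency in what the 80% describes. On either reading that keeps to the protocol's own 40% target or its omnibus hypotheses, the 20% Japanese–Chinese/Korean contrast does not have 80% power at 25 per group. It has about 23–44% if Chinese and Koreans lie between the other two populations. It has about 16% under the omnibus reading if they lie on the other side, and there the 40% pair also misses 80%.

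These figures rest on a 5% level, a common SD, the scales tried and an SD solved backwards. They are not values the protocol yields by itself. Enrolling 40 does not change the conclusion: the extra 15 per group are set aside for exclusions and dropouts, and even if all 40 were analysed the 20% contrast would reach at most 63% in these cases.

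The documents do not show that the sample size is wrong for an omnibus aim, or that the sponsor intends to read a null East Asian result as equivalence. What needs correcting is the stated power, because it determines how much weight such a null result can bear.

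**What to change.** Reword the rationale in section 3.2:

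1. State which test the 80% belongs to, with the SD, scale, direction of the differences and alpha actually used.
2. State separately the power of each named pairwise comparison: Japanese versus Western, and Japanese versus Chinese or Korean. Do the same for East Asian versus Western.
3. Unless the sponsor's SD supports it, remove the 80% for the 20% Japanese–Chinese/Korean difference. Say that this contrast is estimated with a confidence interval, and that a non-significant result does not show absence of a difference.
4. Explain how the 20% used in the calculation fits with the expectation of no difference within East Asia.

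The cost is wording only, with no change to design or enrolment. The stated power for the East Asian contrasts will look less favourable.

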4.4 Procedures for discontinuation/withdrawal

- 1) When discontinuing the study, the principal investigator should promptly explain such a fact to the subject (When the subject requested to terminate the study, the principal investigator should check the detailed reason whenever possible). The principal investigator should also enter information such as the timing of discontinuation/withdrawal and reason in the case report form (CRF).
- 2) When discontinuing the study or withdrawing the subject from the study after the study drug administration, the principal investigator should perform observation in accordance with the Section "8.2.4 Evaluation items for the safety endpoints" (However, 7. Body weight is excluded). Blood sampling for measurements of plasma drug concentrations of the subjects with discontinuation/withdrawn after administration should be carried out only if possible.
- 3) In the presence of adverse events, the principal investigator should investigate until the symptoms resolve or become stable (1 month at the longest).
- 4) When the drop outs take place by discontinuation or withdrawal, additional subjects will not be recruited.

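### Section 3.2 does not show how a CYP3A5*3 frequency of 0.70–0.77 supports 40 per country; if it is an allele frequency, about 20–24 homozygotes remain per East Asian country, below the stated minimum of 25

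*Protocol*

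**What the plan says.** All the relevant text is in the protocol.

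- **Minimum.** In the sample-size rationale of Section 3.2, for 80% power, "the number of subjects was calculated to be at least 25 subjects". The text does not say per group, but 40 per country is described as about 1.5 times this number, so it is read as per group.
- **Inflation.** The target becomes 40 per ethnic population, "considering the subjects excluded from the results of analysis of CYP3A5 to be CYP3A5*3 homo", together with dropouts. Section 3.2 adds that "the target sample size was approximately 1.5 times the number of subjects necessary for statistical analysis" because of ethnic differences in CYP3A5.
- **Evidence for the inflation.** A cited investigation is reported as finding that "the frequency of CYP3A5*3 polymorphism was 0.7 to 0.77 in East Asian population and 0.85 to 0.95 in Caucasian population". No step from this frequency to a share of homozygotes is shown, and no dropout rate is given.
- **Timing.** Section 3.2 places the genotype analysis after the PK analysis, and Section 7.1 takes the genotype sample on Day 2. Homozygotes therefore cannot be selected at entry.
- **Replacement.** Section 4.4: "When the drop outs take place by discontinuation or withdrawal, additional subjects will not be recruited".

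**The concern.** The symbol *3 names an allele. Section 3.2 gives the frequency of the *3 polymorphism in one place and names the homozygous genotype separately in another. A subject is homozygous only if both copies are *3, so an allele frequency has to be squared before it can serve as the share of subjects kept. The inflation factor in the protocol is close to what the unsquared figure gives and smaller than the squared figure requires.

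If the squaring step was missed, the evaluable number in each East Asian country is expected to fall below the protocol's own minimum even with no dropout, and there is no mechanism to make it up. Section 1 says information on East Asian populations is insufficient because Chinese and Korean data are lacking, so the shortfall falls on the groups the study was set up to describe. The sentence on exclusions is also unclear about whether homozygotes are kept or removed, and the two readings give very different numbers.

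**Working it through.** **Inputs from the protocol.** Minimum 25; target 40 per country; factor about 1.5; frequency q = 0.70–0.77 (East Asian) and 0.85–0.95 (Caucasian); differences in AUC0-∞ of 40% (Japanese against Western) and 20% (Japanese against Chinese/Korean); power 80%.

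**Assumed here, because the text at hand does not give them.** Hardy-Weinberg proportions; 10% dropout where stated; two-sided alpha 0.05; a four-group ANOVA; an SD back-solved from n = 25.

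**1. Reproducing the 40.** The minimum of 25 cannot be reproduced without alpha and an SD. The step from 25 to 40 can be approached in two ways:
- Stated factor: 1.5 × 25 = 37.5, that is 38. The actual ratio is 40/25 = 1.6.
- Frequency used directly as the retained share: 25/0.70 = 35.7. With 10% dropout, 35.7/0.90 = 39.7, that is 40.

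The unsquared frequency implies factors of 1/0.77 = 1.30 to 1/0.70 = 1.43 before dropout. The squared frequency implies 1/0.593 = 1.69 to 1/0.49 = 2.04. The stated 1.5 to 1.6 fits the first plus some dropout and falls short of the second.

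**2. Homozygotes expected among 40 if q is an allele frequency (share = q²).**

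| q | q² | 40 × q² | with 10% dropout | P(at least 25 of 40), no dropout |
|---|---|---|---|---|
| 0.70 | 0.490 | 19.6 | 17.6 | 6% |
| 0.77 | 0.593 | 23.7 | 21.3 | 40% |
| 0.85 | 0.7225 | 28.9 | 26.0 | 94% |
| 0.95 | 0.9025 | 36.1 | 32.5 | >99.9% |

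The last column is the exact binomial tail. To leave 25 of 40 on average, q must be at least √(25/40) = 0.79, which is above the quoted East Asian range.

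**3. Enrolment that would leave 25 per East Asian country (25/q², rounded up).** 25/0.593 = 42.2, so 43; 25/0.49 = 51.02, so 52. With 10% dropout: 47 to 57.

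**4. Other readings of the same text.**
- q is already the homozygote share and homozygotes are kept: 40 × 0.70 = 28 to 40 × 0.77 = 30.8 remain. The 40 is adequate.
- q is an allele frequency and homozygotes are removed: 40 × (1 − q²) = 16.3–20.4 East Asians and 3.9–11.1 Caucasians remain.
- q is the homozygote share and homozygotes are removed: 40 × (1 − q) = 9.2–12 East Asians and 2–6 Caucasians remain.

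Only the first of these supports 40.

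**5. Effect on power.** Take means of 0, 0.2, 0.2 and 0.4 for Japanese, Chinese, Korean and Caucasian groups. The SD that gives 80% omnibus power at 25 per group is 0.42 of the reference mean. The noncentral F distribution, with noncentrality Σnᵢ(μᵢ − μ̄)²/SD², then gives:

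| Evaluable per East Asian country / Caucasian | Omnibus power |
|---|---|
| 25 / 25 | 80% |
| 19.6 / 28.9 | 77% |
| 23.7 / 36.1 | 86% |
| 17.6 / 26.0 (10% dropout) | 72% |
| 21.3 / 32.5 (10% dropout) | 82% |

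**The case against.** **The protocol never says allele frequency.** The figures come from a cited investigation that is not available here. If they are homozygote shares, 28–31 of 40 remain and the target stands. This objection holds. It is why the point is conditional and confidence is moderate. It does not remove the need for Section 3.2 to say which frequency it quotes.

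**A reader might infer that the 40 was demonstrably obtained by using the allele frequency unsquared.** The documents do not support that as fact. The match to 40 needs a 10% dropout rate that appears nowhere in the protocol, and 37.5 might simply have been rounded up.

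**A reader might also infer that the study loses its 80% power.** The calculation does not show this. Both power ranges straddle 80%, because the larger Caucasian group partly offsets the smaller East Asian groups. Alpha, SD and effect pattern are assumed as well. What is missed on the allele reading is the stated evaluable minimum.

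**The main comparison may use every dosed subject.** The contents list shows Sections 10.2 and 10.3 on analysis population and items, but their text is not available here, and genotyping follows the PK analysis. On all subjects, 40 exceeds 25. This also stands, so there is no basis for asking the sponsor to change the analysis population. The rationale in Section 3.2 nevertheless justifies 40 by genotype selection, and that is where the gap lies.

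**Conclusion.** The point holds in conditional form. Section 3.2 supports its inflation from 25 to 40 with a frequency whose type it does not state, and with an exclusion sentence that does not make clear who is kept. On the allele reading, which the wording favours, every value in the quoted East Asian range leaves fewer than 25 expected homozygotes per country before dropout. Caucasian numbers are sufficient. Dropouts, which are not replaced, widen the East Asian gap.

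The gap is small at the top of the range (23.7 against 25) and clear at the bottom (19.6). The power consequence is modest and depends on the true frequency. The conclusion rests on Hardy-Weinberg proportions, on the figures being allele frequencies, and on 25 being a per-group requirement for homozygotes. Severity: should-fix, with moderate confidence.

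**What to change.** Keep 40 per country and revise the rationale in Section 3.2:

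1. State whether 0.70–0.77 and 0.85–0.95 are allele or homozygote frequencies.
2. State that CYP3A5*3 homozygotes are the subjects retained, not those removed.
3. If they are allele frequencies, replace the inflation argument with the squared share. Give the expected evaluable numbers (about 20–24 per East Asian country and 29–36 Caucasian, less dropout at a stated rate), and restate the power for those numbers.
4. If the main comparison already uses all dosed subjects, say that the 25 applies to that population. On the allele reading, add that the homozygote analysis is expected to fall below 25 in the East Asian groups.

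The cost is a few sentences and one recalculation, with no extra subjects. On the allele reading the stated East Asian evaluable numbers become less favourable, and the restated power may come out slightly below 80%, depending on the frequency and dropout.
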